## 2.1.1 General definitions

### 2.1.1.1 Study treatment

The following study drugs will be used:

- Investigational treatment
  - Secukinumab prefilled syringes, available as a 150 mg in 1.0 mL and as a 75 mg in 0.5 mL syringes.
- Reference treatment
  - Secukinumab placebo, secukinumab placebo available as 1 mL and 0.5 mL prefilled syringes
  - Etanercept active comparator

The treatment groups for analyses are shown in [Table 2-1](#) and will consider as appropriate. Treatment period up to week 24/52 contains both Induction and Maintenance period.

**Table 2-1 Treatment groups for analyses**

| Treatment group   | Efficacy                  |                          |                                | Safety                    |                                   |                                 |
|---|---------------------------|--------------------------|--------------------------------|---------------------------|-----------------------------------|---------------------------------|
|   | Induction (up to week 12) | Maintenance (week 12-52) | Extension period (week 52-236) | Induction (up to week 12) | Treatment period up to week 24/52 | Entire treatment / study period |
| Low dose Secukinumab (i.e. AIN457 Low dose)                         | X                         | X                        | X                              | X                         | X                                 |                                 |
| High dose Secukinumab (i.e. AIN457 High dose)                       | X                         | X                        | X                              | X                         | X                                 |                                 |
| Placebo   | X                         |                          |                                | X                         |                                   |                                 |
| Placebo to Low dose Secukinumab (i.e. Placebo to AIN457 Low dose)   |                           | X                        | X                              |                           | X a                    |                                 |
| Placebo to High dose Secukinumab (i.e. Placebo to AIN457 High dose) |                           | X                        | X                              |                           | X a                    |                                 |
| Etanercept (max 50mg per dose)                                      | X                         | X                        |                                | X                         | X                                 | X c                  |
| Any Low dose Secukinumab (i.e. Any AIN457 Low dose)                 |                           |                          | X                              |                           | X b                    | X                               |
| Any High dose   |                           |                          | X                              |                           | X b                    | X                               |

|   |  |  |  |   |   |   |
|---|--|--|--|---|---|---|
| Secukinumab (i.e.
Any AIN457 High
dose)     |  |  |  |   |   |   |
| Any Secukinumab
dose (i.e. Any
AIN457 dose) |  |  |  | X | X | X |

a Applicable for safety by-visit analysis

b Not applicable for safety by-visit analysis

c For subsequent analyses beyond the week 52 analysis, Etanercept will only be presented in exposure adjusted incidence rate (EAIR).

For entire treatment period efficacy analysis after week 52; Any AIN457 low dose (without remapping) and Any AIN457 High dose (without remapping) treatment groups will be considered.

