### **6 Visit schedule and assessments**

Subjects should be seen for all visits on the designated day or as closely as possible to the original planned visit schedule.

During the COVID-19 pandemic or similar major health care disruption which limits or prevents on-site study visits, alternative methods of providing continuing care may be implemented such as phone calls, virtual contacts (e.g. teleconsult) or visits by site staff or a home nursing service to the subject's home depending on local regulations and capabilities, that can partially replace on-site study visits, for the duration of the pandemic until it is safe for the subject to visit the site again. These contacts should occur on or around the scheduled visit dates (or more frequently if needed). Every effort should be made to complete all study visit assessments feasible per protocol. Special effort should be made to conduct the scheduled EOT and EOF visits on site. If it is not feasible to conduct these visits on-site, at least phone contact or if possible, visits to the subject's home by site staff as mentioned previously should be attempted.

Screening will be flexible in duration and will last up to a maximum of 4 weeks. During this time, the subject will sign the informed consent form, be evaluated for eligibility and will have all screening visit assessments done as indicated in [Table 6-1](#).

[Table 6-1](#), [Table 6-2](#) lists all of the assessments and indicates with an “x” at which visits the assessments are performed.

If for any reason the subject is a screen failure, the subject may be rescreened. There is no restriction on the number of times a potential subject may be rescreened or on how much time must pass from the date of screen failure and the date of rescreening.

If a subject rescreens for the study, then the subject must sign a new ICF and be issued a new subject number prior to any screening assessment being conducted for the subject under the new screening subject number. For all subjects, the investigator/qualified site staff will record if the subject was rescreened on the rescreening CRF and any applicable screening numbers the subject was issued prior to the current screening number.

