## 7 Safety monitoring

### 7.1 Adverse events

An adverse event (AE) is any untoward medical occurrence (i.e., any unfavorable and unintended sign [including abnormal laboratory findings], symptom or disease) in a subject or clinical investigation subject *after providing written informed consent* for participation in the study. Therefore, an AE may or may not be temporally or causally associated with the use of a medicinal (investigational) product.

The occurrence of adverse events should be sought by non-directive questioning of the patient at each visit or scheduled phone contact during the study. Adverse events also may be detected when they are volunteered by the patient during or between visits or through physical examination, laboratory test, or other assessments.

Abnormal laboratory values or test results constitute adverse events only if they fulfill at least one of the following criteria:

- they induce clinical signs or symptoms,
- they are considered clinically significant,
- they require therapy.

Clinically significant abnormal laboratory values or test results should be identified through a review of values outside of normal ranges/clinically notable ranges, significant changes from baseline or the previous visit, or values which are considered to be non-typical in patient with underlying disease. Investigators have the responsibility for managing the safety of individual patient and identifying adverse events. Notable ranges for labs values are included in [Appendix 1](#).

Adverse events should be recorded in the Adverse Events CRF under the signs, symptoms or diagnosis associated with them, accompanied by the following information.

- the severity grade
  - mild: usually transient in nature and generally not interfering with normal activities
  - moderate: sufficiently discomforting to interfere with normal activities

- severe: prevents normal activities.
- its relationship to the
  - study treatment (no/yes), or
  - investigational treatment (no/yes), or
  - the other study treatment (non-investigational) (no/yes), or
  - both or indistinguishable
- Its duration (start and end dates) or if the event is ongoing an outcome of not recovered/not resolved should be reported.
- whether it constitutes a serious adverse event (SAE - See [Section 7.2](#) for definition of SAE)
- action taken regarding [study/investigational] treatment (*select as appropriate*)

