### **Treatment groups for evaluation**

The summaries of evaluation will be reported for both induction period and entire treatment period or up to week 24 maintenance period will also be reported, for Week 24 PEA. Treatment period up to week 52 including both induction period and maintenance period will be reported for week 52 analysis. A number of selected safety analyses will be reported for entire study period, which covers the study period from randomization to end of study. The treatment following groups will be used:

- for induction period:
  - AIN457 Low dose, AIN457 High dose, Placebo, Etanercept;
- for maintenance treatment period (or up to week 24/52):
  - by-visit summary: AIN457 Low dose, AIN457 High dose, Placebo to AIN457 Low dose, Placebo to AIN457 High dose, Etanercept, Any AIN457 dose.
  - by-period summary: AIN457 Low dose, AIN457 High dose, Any AIN457 low dose, Any AIN457 high dose, Etanercept, Any AIN457 dose.
- for entire treatment/study period:
  - Any AIN457 low dose, Any AIN457 high dose, Any AIN457 dose, Etanercept\*.

\*Of note, for subsequent analyses beyond week 52 analysis, Etanercept will only be presented in EAIR

Safety analyses will be performed on treatment received or actual treatment (See [Section 2.2: Safety set](#)).

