## **2.15.5 Interim analysis**

[figure not shown]
Apart from the final analysis, the study is also planned with two full analyses.

The first full analysis will be performed when all patients completed the Week 24 visit. And the next full analysis will be performed when all patients completed the Week 52 visit (i.e. Maintenance period).

The data cut-off date for the Week 24 PEA is the date of the last Week 24 visit for study subjects, i.e. 7 March 2019. The Week 24 PEA will include all efficacy data up to week 24

visit for each individual subject. For inclusion of safety data, we apply individual data cut-off of each subject to maximize use of available data. Thus for each subject, we will include all safety data collected until the last visit of the subject prior to the PEA data cut-off of 7 March 2019.

The data cut-off date for the Week 52 interim analysis is the date of the last Week 52 visit for study subjects, i.e. 18 September 2019. The Week 52 interim analysis will include all efficacy data up to week 52 visit for each individual subject. For inclusion of safety data, we apply individual data cut-off of each subject to maximize use of available data. Thus for each subject, we will include all safety data collected until the last visit of the subject prior to the interim analysis data cut-off of 18 September 2019.

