## 5.1.4 Exposure adjusted incidence rate and related risk estimates

### 5.1.4.1 Exposure adjusted incidence rate and 100\*(1- $\alpha$ )% confidence interval

[figure not shown]
It will be assumed that for each of  $n$  subjects in a clinical trial the time  $t_j$  ( $j=1, \dots, n$ ) to the first occurrence of a certain treatment emergent event is observed, or if the event was not experienced, the (censored) time to the end of the observation period or last dose plus 84 days whichever occur earlier. The sequence of first occurrences of an event will be modelled to follow approximately a Poisson process with constant intensity  $\theta$ . The rate parameter  $\theta$  will be estimated as  $\lambda=D/T$ , where  $T = \sum_{j=1}^n t_j$  and  $D$  is the number of subjects

with at least one event. Conditionally on T, an exact  $100*(1-\alpha)\%$  confidence interval for a Poisson variable with parameter  $\theta T$  and observed value D can be obtained based on [Garwood, 1936](#), from which an exact  $100*(1-\alpha)\%$  confidence interval for D/T will be derived as follows ([Sahai, 1993](#); [Ulm, 1990](#)):

$$\text{Lower confidence limit } L = \frac{0.5c_{\alpha/2,2D}}{T} \text{ for } D>0, 0 \text{ otherwise,}$$

$$\text{Upper confidence limit } U = \frac{0.5c_{1-\alpha/2,2D+2}}{T}$$

where  $c_{\alpha k}$  is the  $\alpha$ th quantile of the Chi-square distribution with k degrees of freedom.

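### After the Week 52 analysis, etanercept and secukinumab safety rates are set side by side over windows of about 1.2 and up to 4.7 years, which is a fair reading only if the hazard is roughly constant

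*SAP*

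**What the plan says.** SAP 2.1.1.1, Table 2-1, footnote c: "For subsequent analyses beyond the week 52 analysis, Etanercept will only be presented in exposure adjusted incidence rate (EAIR". SAP 2.9 (Treatment groups for evaluation) repeats the rule and lists the columns for the entire treatment and study periods as "Any AIN457 low dose, Any AIN457 high dose, Any AIN457 dose, Etanercept".

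SAP 5.1.4.1 defines the rate as D/T. D is the number of subjects with at least one event, and T sums the time to first event or to censoring at the end of observation or 84 days after the last dose, whichever is earlier. The model is explicit: "The sequence of first occurrences of an event will be modelled to follow approximately a Poisson process with constant intensity".

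The two drugs are followed for very different times. Protocol Table 6-1 (footnote 15) ends etanercept at Week 51, and Protocol 3.1 bars etanercept patients from the extension. Protocol 5.2 continues secukinumab to Week 232.

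SAP Table 2-11 plans exposure-adjusted rates only for the entire treatment and entire study periods. For induction and for the period up to Week 52 it gives crude incidence. No exposure-adjusted rate on a common window, and none by year of exposure, is planned.

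**The concern.** D/T removes the effect of follow-up length only when the hazard is constant. Otherwise it is an average over the window, and two drugs with identical risk over time get different rates because one was watched longer. Three features of this trial make a constant recorded hazard doubtful.

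- **Contact thins out.** Events are "sought by non-directive questioning of the patient at each visit" or at scheduled phone contacts (Protocol 7.1). Protocol Table 6-1 has 19 site visits after randomisation up to Week 52. Table 6-2 has 4 in the next 52 weeks (Weeks 64, 76, 88 and 104).
- **First-event counting.** If children differ in susceptibility, those who react early leave the risk set, and later person-time comes mainly from lower-risk children.
- **Calendar time.** The Week 52 cut-off "is the date of the last Week 52 visit for study subjects, i.e. 18 September 2019". Later follow-up is therefore secukinumab extension time or off-treatment follow-up, and part of it falls in the COVID-19 period, when Protocol 6 allows alternative contacts "that can partially replace on-site study visits".

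Etanercept is the only active safety reference, so readers will compare its column with secukinumab's even though no test is planned. The Week 52 analysis does not supply a matched rate either. SAP 2.15.5 includes each child's safety data up to the cut-off date, so early secukinumab enrollees already contribute extension time.

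**Working it through.** **Inputs from the documents**
- Timeline check: 12 + 40 + 184 = 236 weeks, and 236 × 7 + 1 = Day 1653, as in SAP Table 2-2a.
- Etanercept: Week 51 is Day 358; 358 + 84 = Day 442, or 442/365.25 = 1.21 years (about 63 weeks).
- Secukinumab: Week 232 is Day 1625; 1625 + 84 = Day 1709, or 4.68 years (about 244 weeks).

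**Assumed, because the documents give no values:** 0.02 to 2 first events per patient-year; constant hazard; gamma frailty variance 0.5 or 1; or recorded hazard multiplied by 0.5, 0.7 or 1.3 after year 1.

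**Formula.** With event-free probability S(t) and window τ, the expected rate is (1 − S(τ)) / ∫₀^τ S(t) dt. The same S(t) is used for both drugs, so a ratio other than 1 comes only from the windows.

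**Constant hazard λ.** The integral is (1 − e^(−λτ))/λ, so the rate is λ for any τ and the ratio is exactly 1.00.

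**Frailty example (variance 1, 0.5 per year).** S(t) = 1/(1 + 0.5t) and the integral is ln(1 + 0.5τ)/0.5.
- Etanercept: S(1.21) = 1/1.605 = 0.623; integral 0.946; rate 0.377/0.946 = 0.398.
- Secukinumab: S(4.68) = 1/3.34 = 0.299; integral 2.41; rate 0.701/2.41 = 0.290.
- Ratio: 0.290/0.398 = 0.73.

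**Secukinumab/etanercept ratio at study end, equal true risk**

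| Hazard | 0.02/yr | 0.1/yr | 0.5/yr | 1/yr | 2/yr |
|---|---|---|---|---|---|
| Constant | 1.00 | 1.00 | 1.00 | 1.00 | 1.00 |
| Frailty variance 0.5 | 0.98 | 0.93 | 0.83 | 0.80 | 0.81 |
| Frailty variance 1 | 0.97 | 0.88 | 0.73 | 0.69 | 0.67 |
| ×0.5 after year 1 | 0.67 | 0.68 | 0.72 | 0.79 | 0.91 |
| ×0.7 after year 1 | 0.81 | 0.81 | 0.85 | 0.90 | 0.96 |
| ×1.3 after year 1 | 1.17 | 1.16 | 1.11 | 1.06 | 1.02 |

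If secukinumab is cut at Week 104, the ratios for 0.1 to 2 per year are 0.86 to 0.98 under frailty and 0.83 to 0.97 under a falling hazard.

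**The 84-day tail.** It is 84/442 = 19% of the etanercept window but 84/1709 = 5% of the secukinumab window. If half or all of the risk stops with the drug, otherwise constant, the study-end ratio is 1.03 to 1.18 for 0.1 to 2 per year, which counts against secukinumab.

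**Does a common window repair it?** A simulation used 40 etanercept patients, 80 randomised to secukinumab and an assumed 38 placebo switchers, with equal risk, frailty variance 0 to 2 and 4,000 runs per scenario. Cutting secukinumab at 442 days gave ratios of 0.97 to 1.00, and secukinumab had the lower rate in 47% to 52% of runs. With the unequal windows and frailty variance 0.5 to 2, it had the lower rate in 54% to 98%.

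**The case against.** A reader might infer that these tables make secukinumab look safer than etanercept. The documents do not support that. Under the SAP's own constant-intensity model there is no distortion. A rising hazard, or risk that ends with the drug, reverses the sign, and the tail effect can be as large as the frailty effect at Week 104.

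The ascertainment argument also has limits. Protocol 7.1 includes scheduled phone contacts and events volunteered between visits. Protocol 6.5 keeps pandemic contacts on or around the scheduled dates, or more often, with case report forms updated. Fewer visits do not shorten time at risk, and nothing in the documents supports a 30% or 50% fall in recorded hazard.

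The consequence is bounded. Protocol 3.4 rules out a formal comparison with etanercept, and the safety objective is worded against placebo. The Week 52 crude tables already give a matched period with the randomised dose groups and etanercept. Footnote c itself removes etanercept's crude percentages from later tables, where unequal follow-up would distort them directly.

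Precision is low as well. At 0.1 per year, 40 × (1 − e^(−0.121)) ≈ 4.6, so about 5 first events on etanercept; 5 events give an exact 95% interval of about 0.32 to 2.33 times the estimate. A frailty shift of 7% to 12% sits well inside it.

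All of this stands. It removes any claim about direction and lowers the stakes. It does not make the post-Week 52 rates comparable, and the crude Week 52 tables are not a matched exposure-adjusted rate.

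**Conclusion.** The point holds in neutral form. Etanercept and secukinumab rates over about 1.2 and up to 4.7 years can be read against each other only if the hazard is roughly constant, and the thinner visit schedule and first-event counting make that doubtful. A recorded hazard that falls after year 1 favours secukinumab. One that rises, or risk that stops with the drug, disfavours it.

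With equal true risk and 0.1 to 2 events per year, the study-end ratio is 0.67 to 0.93 under frailty variance 0.5 to 1, 0.68 to 0.96 with hazard ×0.5 to ×0.7 after year 1, 1.00 under constant hazard, and 1.02 to 1.16 with hazard ×1.3. At 0.02 per year frailty moves the ratio only 2% to 3%, although a drop in recording would still matter there (0.67 to 0.81). Event rates, frailty variances and hazard multipliers are all assumptions, so neither size nor net direction can be settled from the documents. The matter affects the interpretation of descriptive safety tables, not any planned test.

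**What to change.** In SAP 2.1.1.1 (Table 2-1, footnote c), SAP 2.9 and Table 2-11:

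1. Add exposure-adjusted rates for all arms censored at one common point: first dose to Week 52, or the same 63-week limit.
2. Name these as the rates to be read against etanercept in every report after Week 52.
3. Give later secukinumab rates by year of exposure.
4. Where a whole-period table keeps the etanercept column, add a note that the windows differ and state their lengths.

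This needs no new data, only one censoring rule and a change of table layout, and it works whichever way the hazard moves. The price is less secukinumab person-time and wider intervals in the matched comparison.

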### 2.1.1.2 Study Day 1 and other study days

The first day of administration of randomized study treatment (first dose) is defined as Study Day 1 or Day 1.

All other study days will be labelled relative to Day 1. For event dates on or after Day 1, study day for a particular event date is calculated as [Date of event] – [Date of first dose]+1, i.e., Day 2, Day 3, etc., will be one day, two days, etc., after Day 1, respectively. For the dates before Day 1, study day for an event date is calculated as [Date of event] – [Date of first dose], i.e., Day -1, Day -2, etc., will be one day, two days, etc., before Day 1, respectively. Duration of an event will be calculated as (Event end date – Event start date + 1).

The descriptor “Day 0” will not be used.

### 2.1.1.3 Screening, baseline and post-baseline definitions

*Screening* refers to any procedures (e.g., checking inclusion and exclusion criteria) performed prior to the date of first dose of study treatment (for safety analysis) or prior to the randomization date (for efficacy analysis). Per protocol, subject informed consent must be obtained prior to performing any study related activity. The date of signing informed consent is the start date of screening period. Any assessment obtained during the screening period will be labelled screening assessment. Assessments made on Day 1 may occur before or after the randomization or the first dose.

For efficacy analyses, baseline is the last assessment (including unscheduled visits) obtained on or before the randomization (day). All assessments obtained after randomization (day) are considered as post-baseline unless otherwise specified.

For safety analyses, baseline is the last assessment (including unscheduled visits) obtained (on or) before the first dose (day) of study treatment. All assessments obtained after the first dose (day) of study drug are considered as post-baseline unless otherwise specified.

In general, a baseline value refers to the last measurement made prior to administration of the first dose of study treatment. However, for Quality of Life assessments, Lab and ECG, if no pre-treatment value exists, values recorded after first dose of treatment can be used as baseline only if it was collected on the same day as first dose.

Of note, baseline will be derived based on the randomization day or first dose day, exact randomization/dosing time is not considered. And “re-randomization” for placebo group at Week 12 will not be used for baseline definition and only one baseline value will be defined referring to the first randomization.

#### 2.1.1.4 Day of last dose of randomized study treatment

The date of last dose will be collected via the CRF. The subject's exposure will be calculated considering the end of treatment period visit. The end of treatment period will be defined as the last dose plus 84 days or last visit whichever occurs earlier. i.e., for subjects who discontinued or have their last visit earlier than last dose plus 84 days, the end of study treatment exposure will be the date of the last study visit in the corresponding treatment period.

On-treatment event is defined as assessments within last dose plus 84 days, for safety analysis (i.e., Lab, vitals and ECG).

